Humulin® R U-500 is a concentrated formulation of a polypeptide hormone structurally identical to human insulin. Developed using rDNA technology, the product has been marketed since 1996 in 20 mL vials, indicated to improve glycemic control in adults and children with diabetes mellitus requiring more than 200 units of insulin per day.¹ It has proven to be of particular benefit for patients with insulin resistance because the concentrated formulation allows for delivery of a higher dose in a reasonable volume. As insulin resistance worsens, greater doses are required to meet glycemic goals and patients may face challenges in subcutaneous administration of their medicine.²

Although the concentrated formulation has been shown to be safe and effective when used as directed, there have been serious medication errors with Humulin® R U-500 in the past. ^{1,3,4} Errors have been attributed to dispensing, prescribing, and administration. The majority of instances have resulted from dosing confusion, with the most serious events occurring among patients who experience hypoglycemia from overdosing. Less frequent serious adverse events have been attributed to failures of glycemic control due to underdosing or from drug-drug interactions.

In April 2016, Eli Lilly and Company (Lilly) launched the 3 mL Humulin[®] R U-500 KwikPen[®] (prefilled pen containing 1,500 units of insulin). The new combination product uses Lilly's established KwikPen technology.

The KwikPen is anticipated to mitigate risks for dosing errors with the U-500 concentration. But changes to product labeling in July 2016 include new information healthcare professionals (HCPs) must be familiar with for informing their patients about safe use. The package insert and information disseminated to providers draws on experience with the KwikPen application to date. For example, human factors studies sponsored by Lilly showed that a small percentage of patients may choose to withdraw concentrated insulin from the pen cartridge with a syringe in cases of device malfunction. Likewise, anecdotal information suggested that patients could transfer insulin from the pen cartridge into an insulin pump.

This study is an initial evaluation of the effectiveness of a risk minimization plan (RMiP) conducted within 18-months of product launch, designed to meet a post-market commitment to the Food and Drug Administration (FDA) for the new KwikPen combination product. The study focuses on Lilly's communication with HCPs, and specifically prescribers (endocrinologists and prescribing primary care physicians, nurse practitioners, and physician's assistants). Through an online survey, the study will query knowledge of and outcomes related to the Dear Health Care Provider (DHCP) letter (Appendix I) sent to prescribers and pharmacists following the product launch. The DHCP letter is intended to alert HCPs of the risks associated with Humulin[®] R U-500 KwikPen[®].

Early evaluation of communications constituting part of risk mitigation measures have evolved toward an emphasis on process measures. This is important because it may be difficult to detect actual impacts on relatively low-frequency medication errors across the first year or longer of an intervention. Surveys, particularly those conducted closely following implementation, focus on the extent to which the program has been executed, the intended impacts on behavior, and assessments of clinical knowledge or comprehension of risks contained in the communication. The FDA has recommended a knowledge, attitudes, and behavior survey (KAB) as a sufficient assessment tool in most cases.⁵

This KAB survey is designed to capture three of four elements appropriate to learning evaluations identified by the FDA: ⁶

- *Reaction* How satisfied are physicians with communications materials, and did they actually receive and utilize them?
- Learning What knowledge about risks have they learned or had reinforced, and how comprehensible are the key messages about risks and the need to communicate those risks to patients?
- *Planned Behavior* What changes (or intention to change) do physicians make in the areas of patient instruction and recognizing the significant potential for dosing error leading to hypoglycemia incidence?

The objectives of the fourth element *Results* (collecting concrete public health outcomes of interest such as reductions in medication dosing errors), exceed the scope of a survey of this type. Additionally, 18 months may be an insufficient period for detecting informative and compelling results on actual risk reduction.

5 Research Question and Objectives

The research questions motivating this study relate to how well the distribution of the DHCP letter has proceeded in the early post-launch period and how well that communication material conveys the most significant risks of Humulin[®] R U-500 KwikPen[®] to prescribers. The study also evaluates prescriber understanding about important patient education about those risks. As noted above, this early evaluation focuses on process measures related to reaction, learning, and planned behavior.

The primary study objective is to evaluate the impact of the DHCP letter on prescriber understanding about the risk of hypoglycemia and educational points to be emphasized in discussion with patients.

Retention and comprehension by HCPs of the following specific key safety messages will be tested in line with this objective. Specifically, HCPs should:

- only consider prescribing Humulin[®] R U-500 KwikPen[®] to patients needing more than 200 units of insulin per day.
- specify the prescribed dose in units of insulin (5-unit increments) on the prescription.
- inform patients of their dose in units of insulin.
- educate patients that no dose conversion is needed with Humulin[®] R U-500 KwikPen[®] and that the dose window shows the number of units to be injected.
- educate patients not to withdraw Humulin[®] R U-500 insulin from the KwikPen[®] with a syringe.
- instruct patients to maintain backup Humulin® R U-500 KwikPen®.
- instruct patients in the event of a malfunction, to use their backup pen or contact a pharmacist, healthcare professional, or The Lilly Answers Center for more information at [name].
- teach patients not to count clicks to determine their dose when using Humulin[®] R U-500 KwikPen[®].

The secondary objectives include

- assessing the proportion of HCPs receiving and reading the DHCP letter and their reactions to the risk mitigation communication content.
- querying prescriber intentions regarding patient education around safe use of the Humulin[®] R U-500 KwikPen[®].

6 Research Method

6.1 Study design

This is a cross-sectional survey to be conducted in the United States. Eligible HCPs will have received the DHCP letter in April 2016 and subsequently prescribed the Humulin[®] R U-500 KwikPen[®]. The HCPs who received the DHCP letter include endocrinology specialists, primary care physicians, advanced practice registered nurses, nurse practitioners, and physician assistants who have prescribed Humulin[®] U-500 (in vial dosage forms) during the 12 months prior to the Humulin[®] R U-500 KwikPen[®] product launch. A random sample of HCPs will be recruited to participate in the survey from the list of HCPs who received a DHCP letter via email. The HCP survey will be administered online.

6.2 Setting

The assessment survey will be executed and the analysis completed within approximately 18 months of the product launch.

Eligible HCPs will receive an invitation to participate via email that includes a link to the survey (Appendix II). The invitation will include an overview of the rationale for the survey, information on how to access and complete the survey online, and privacy information. The average survey is expected to take approximately 15 minutes to complete.

The invitation will also indicate that HCPs will be compensated with an incentive card having a \$50 value. All those providing screening information are eligible, with the exception of HCPs who are licensed and practice in Minnesota, Vermont, Massachusetts or the District of Columbia and Advanced Practice Registered Nurses (APRNs) in Connecticut in accordance with state laws. HCPs from these states can elect to participate, although they will not be paid. HCP-identifying information will be utilized for the purposes of providing payment and will be managed by a third party vendor, Schlesinger Associates (SA).

HCPs eligible for compensation, who complete the screening questions, will be mailed their honorarium. Additionally, HCPs will be emailed a letter thanking them for their time and effort. The email will also include a link to the DHCP letter on the correct use of Humulin[®] R U-500 KwikPen[®] and a link to the correct answers to key safety message questions (Appendix III).

6.2.1 Population

The initial population in scope for selection consists of the 15,179 HCPs who were sent a DHCP letter and prescribe the Humulin[®] R U-500 KwikPen[®] within 12 months of the launch date. The sampling frame is limited to the 10,442 HCPs (69%) who have a valid email, as recruitment will be implemented via email only.

Initially 1,000 HCPs will be randomly selected in order to obtain 200 completed surveys with a target response rate of 20%. The response rate will be monitored throughout the data collection period of 3-5 months. Of the 1000 initially sent, if any are undeliverable, they will be replaced.

Follow-up via phone or email or randomly selecting additional HCPs will be assessed as options to obtain 200 completed surveys if the initial response rate is lower than 20%. If the response rate is higher than 20% then no follow-up or additional HCP sample will be required.

HCPs who complete the screener and qualify for the survey are included in the survey's analysis population. Data collected on the screener and on the survey will be available for this analysis population.

HCPs who complete the screener, but do not qualify to participate in the survey are included in the screen failures analysis. These HCPs may fail the screener because they indicate that they have not met one of the inclusion/exclusion criteria. Data collected on the screener will be available for this population.

6.2.2 Inclusion Criteria

HCPs must meet the following criteria to be eligible for inclusion in the survey:

- HCPs who received the DHCP letter.
- HCPs who prescribed the insulin product Humulin[®] R U-500 KwikPen[®].
- HCPs must be able to read and respond to the survey in English.

6.2.3 Exclusion Criteria

HCPs meeting any of the following criteria will not be included in the survey:

- HCPs or their immediate family members are current or past employees of Lilly, Covance, SA, or the FDA.
- HCPs have participated in this Humulin[®] R U-500 KwikPen[®] survey before.

6.2.4 Survey Period

A 3-5 month data collection is estimated to recruit the HCPs and obtain approximately 200 completed surveys.

6.3 Variables

As specified in the project objectives above, the survey captures HCPs' knowledge of the key safety messages in the risk minimization communication letter as primary outcomes. While these questions contain an option for "I don't know," response will be dichotomized for analysis as correct or incorrect across seven statements. An additional multiple-choice item provides three correct options with an incorrect choice outlining an unsafe practice for dealing with KwikPen malfunction. HCPs will also be asked about the source of their knowledge of product risks, using a single multiple choice question.

Additionally, the survey instrument has questions about the HCP's reaction to the communication. Recall of receipt of the DHCP letter is required for participation in the study. Additional reactions are queried in a series of four questions with Likert response scales for those confident about having read the material. As there are no correct answers for these appraisals of the DHCP letter, responses will be analyzed descriptively.

Finally, the HCP survey includes a question that queries planned behavior. The item asks about the prescriber's knowledge about the need for patient counseling by prescribers; it is a multiple choice question that can also be dichotomized to correct or incorrect response.

The survey also captures demographic characteristics that include age, gender, geographical location, HCP specialty, and practice information. Personal contact information about an HCP will only be collected by SA where applicable for mailing payment to study participants; this information will not be included in study datasets.

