6.7.1 Analysis Data Sets

The Analysis Set will consist of all eligible HCPs who undertake the survey. The Analysis Set will be used to assess all the study objectives unless otherwise stated.

The Screening Set will consist of all HCPs identified as being ineligible for reasons other than immediate refusal to participate or prior participation. Demographic information will be presented for the Screening Set.

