6.9 Limitations of the Research Methods

The sample is subject to volunteer bias because HCPs decide independently whether or not to respond to the invitation to participate. There is no active follow-up to the recruitment invitation planned. To moderate the impact of self-selection, HCPs will be randomly selected from the list of HCPs who received the DHCP letter, which should be generalizable to the overall HCP population who are educated about the use of Humulin[®] R U-500 KwikPen[®].

Additionally, the participation in the survey is reliant on the HCP's recall of whether or not the DHCP letter was received. However, it is possible that HCPs may simply not recall receiving the materials that were, in fact, received. It is also possible that they have acceptable understanding of the risks and appropriate behaviors despite not having read the DHCP letter. Lilly will explore the latter possibility with variables described in Section 6.3.

As with most survey data, information is self-reported and therefore susceptible to reporting biases. There may ultimately be discrepancies between what HCPs report about their intentions and what they ultimately do.

Lastly, this survey is administered only online. While the majority (69%) of the HCPs on the sampling frame (see Section 6.2.1) provided an email address, not everyone on the list has an email address listed. This could introduce additional selection bias.

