[PROGRAMMING NOTE: Include logic to insert region for all locations based on selection]
5. What is your role in the management of patients with diabetes?
₁ ☐ Physician
2 ☐ Advanced Practice Registered Nurse
3 ☐ Nurse Practitioner

4 ☐ Physician Assistant 5 ☐ Other
6. Please choose an option about your participation in this survey.
 I will participate in the survey and would like to be paid. I will participate in the survey but will not to be paid.
[PROGRAMMING NOTE: Compensation for participation is not permitted for HCPs in Vermont, District of Columbia, Massachusetts, or Minnesota, as well as, for Advanced Practice Registered Nurses (APRNs) in Connecticut. HCPs should be advised that they are ineligible for payment based on these restrictions, if appropriate.]
7. Are you involved in the management of patients with diabetes? This includes prescribing medications to treat diabetes or providing education to help manage diabetes.
1 ☐ Yes 2 ☐ No [PROGRAMMING NOTE: If participant answers "2", then go to Q7 and terminate after Q14.
8. What is your primary medical specialty?
☐ General Internal Medicine ☐ Endocrinology/Diabetology ☐ Family Medicine ☐ Other
9. How many years have you been in practice as a physician, physician assistant, or nurse practitioner since completing your medical/nursing education?
 Less than 5 years □ 5 - 10 years □ 11 - 15 years □ More than 15 years

Study Protocol for $Humulin^{\it @}$ R U-500 $KwikPen^{\it @}$

10. In what type of facility do you work?
☐ General Practice ☐ Hospital ☐ Other
11. Approximately, how many patients have you prescribed the Humulin [®] R U-500 KwikPen [®] ?
1 □ 0 2 □ 1 - 5 3 □ 6 - 10 4 □ 11 - 20 5 □ More than 20
[PROGRAMMING NOTE: If participant answers "0", then terminate after Q14.]
12. Which of the following age groups best describes you?
1 ☐ Less than 30 2 ☐ 30 – 39 3 ☐ 40 – 49 4 ☐ 50 – 59 5 ☐ 60 – 69 6 ☐ 70 or older
13. What is your gender?
1 ☐ Male 2 ☐ Female
14. Are you aware that you received a Dear Health Care Provider letter from Eli Lilly and Company about the Humulin [®] R U-500 KwikPen [®] system?
1 ☐ Yes 2 ☐ No 3 ☐ I don't know
[PROGRAMMING NOTE: If participant answers "2" or "3", then terminate.]
[PROGRAMMING NOTE: End of screening questions]

Study Protocol for $Humulin^{\it @}$ R U-500 $KwikPen^{\it @}$

[PROGRAMMING NOTE: Begin survey questions]

Survey

The following questions are about Humulin® R U-500 KwikPen®.

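### Recall of the DHCP letter is both an entry condition and an outcome: receipt is 100% by design in the Analysis Set, and the knowledge results cover only prescribers who say they recall it

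*Protocol*

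**What the plan says.** - **Entry condition.** Section 6.3: "Recall of receipt of the DHCP letter is required for participation in the study". Awareness of receipt is also in the 6.4 list of screening questions. In Appendix II, Q14 asks "Are you aware that you received a Dear Health Care Provider letter from Eli Lilly and Company"; No and I don't know both end the survey. Q14 is the last screening item, so those stopped there never see the knowledge items (Q15 and Q16).
- **Outcome.** Section 5 gives a secondary objective of "assessing the proportion of HCPs receiving and reading the DHCP letter and their reactions to the risk mitigation communication content". Section 6.4 lists awareness of the letter first among the data used to evaluate effectiveness.
- **Analysis population.** Section 6.7.1: "The Analysis Set will be used to assess all the study objectives unless otherwise stated". For those found ineligible, the same section says only that "Demographic information will be presented for the Screening Set". The primary denominator in 6.7.4 is HCPs who complete the survey, and the plan counts as effective if a majority of HCPs answer the key statements correctly.
- **Frame.** Under 6.2.1 the sample comes from 10,442 HCPs with a valid email, out of 15,179 who were sent the letter and prescribe the KwikPen.
- **Acknowledged limitation.** Section 6.9 notes that participation relies on recall: "However, it is possible that HCPs may simply not recall receiving the materials that were, in fact, received".

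**The concern.** A variable that decides who enters the analysis cannot also be estimated in that analysis. With the Analysis Set as the default, the receipt part of the secondary objective is a constant, and the reading part is a proportion among recallers presented as a proportion of HCPs.

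The primary endpoints are affected too. Section 5 asks how well distribution of the letter has gone and what impact the letter had on prescriber understanding. A prescriber who was sent the letter and has no memory of it is informative on both questions, and is dropped before the first knowledge item. The percentages and the effectiveness conclusion then describe a narrower group than the one sampled. The comparison by recall, the nearest thing to a contrast within this survey, is lost as well.

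A later analysis plan could redefine the receipt denominator. It could not supply knowledge answers from people who were never asked.

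**Working it through.** **1. The plan's own precision figure.** Section 6.5 gives ±5.49 points for n = 200, 80% correct and N = 10,000. With the square root taken over the whole finite-population ratio:

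1.96 × √(0.8 × 0.2 / 200) × √(9,800 / 9,999) = 0.05544 × 0.9900 = 5.49 points. It reproduces.

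**2. Receipt in the Analysis Set.** Everyone in the set answered Yes at Q14, so the proportion is 200/200 = 100% and the same formula gives a half-width of 0. It carries no information.

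**3. Receipt among those who answered Q14.** This is estimable. Let r be the share recalling receipt. The protocol gives no value, so r is assumed. Reaching 200 recallers needs 200/r HCPs screened:

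| Assumed r | Screened for 200 recallers | Half-width for r (points) |
|---|---|---|
| 0.3 | 667 | 3.4 |
| 0.5 | 400 | 4.8 |
| 0.7 | 286 | 5.2 |
| 0.9 | 223 | 3.9 |

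**4. Possible overstatement of knowledge.** If recallers exceed non-recallers by a gap g, the value among all those screened is r × (recallers) + (1 − r) × (recallers − g). The recaller figure is therefore too high by (1 − r) × g. Both r and g are assumptions:

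| | g = 10 | g = 20 | g = 30 |
|---|---|---|---|
| r = 0.7 | 3 | 6 | 9 |
| r = 0.5 | 5 | 10 | 15 |
| r = 0.3 | 7 | 14 | 21 |

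The range is 3 to 21 points, against a planned half-width of 5.49.

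**5. Effect on the majority criterion,** read here as more than 50%. Starting from an assumed 85% among recallers, the worst cell gives 85 − 21 = 64%, still a majority. To reach 50% at r = 0.3, non-recallers would have to be at (0.50 − 0.3 × 0.85) / 0.7 = 35%, a gap of 50 points. Starting from 80%, the tipping value is (0.50 − 0.24) / 0.7 = 37% at r = 0.3, and (0.50 − 0.40) / 0.5 = 20% at r = 0.5. At r = 0.7 it cannot be reached, because recallers alone contribute 0.7 × 80 = 56%.

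**6. Time to recall.** The letter went out in April 2016 (6.1) and data collection is planned for July to October 2017 (section 3). Recall is therefore asked 15 to 18 months later, so some loss of recall is to be expected, but this does not fix r.

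**The case against.** - **The receipt proportion is not lost.** A reader might infer that the secondary objective cannot be answered at all. The documents do not support that. Screener data are kept for screen failures (6.2.1), and ineligible HCPs are reported with reasons (6.7.2), so a recall proportion can be recovered. This stands, but no text makes that proportion the endpoint. The 6.7.2 percentages are based on all responders, including people stopped before Q14. Respondents with no KwikPen prescriptions do reach Q14 but are not in the target group.
- **Asking about receipt operationalises an inclusion criterion.** Section 6.2.2 requires receipt, and being on the list shows only that a letter was sent. Limiting the study to recipients is a legitimate choice of target population. Q14, however, is unverified self-report and measures recall. A reader might infer that the analysed prescribers are those the letter demonstrably reached. That does not follow either: Q18 lets the same respondents say they did not read it or do not recall reading it, and 6.7.5 expects such people.
- **The direction of bias is not shown.** Section 6.9 allows for good understanding without reading the letter, and Q17 lists other sources such as the package insert and sales representatives. This stands: overstatement is plausible, not proven.
- **The limitation is disclosed.** Section 6.9 does so, but changes neither the objective nor the analysis set. Its intention to explore understanding without reading can be met only among recallers.
- **Question order.** A reader might also see Q14's position as breaching 6.8. It does not: 6.8 places the reading and reaction questions after the risk questions, and Q18 and Q19 are there.

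**Conclusion.** The point holds without any assumed figure. As written, receipt is 100% in the set designated for all objectives, reading is conditional on recall, and the primary percentages and effectiveness conclusion apply only to prescribers who say they recall the letter. Section 6.9 discloses the dependence on recall without resolving it.

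The numerical effect on knowledge is unknown. The 3 to 21 points rest on assumed recall of 30% to 70% and an assumed gap of 10 to 30 points, neither of which the protocol supports with data. A reader might infer that the majority conclusion is unsafe. Within those ranges and from 85% among recallers it survives, at 64% or more, and overturning it needs a gap well outside them. What needs correcting is the mismatch between objective, denominator and population.

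**What to change.** **Preferred.**
- Delete the terminate instruction after Q14 and ask Q14 after the knowledge items, just before Q18.
- Define the first inclusion criterion in 6.2.2 as being on the DHCP distribution list.
- Remove the recall requirement from 6.3 and the awareness item from the 6.4 screening list.
- Report receipt (Q14) and reading (Q18) over all KwikPen prescribers who complete the survey, and the primary endpoints overall and by Q14 answer.

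**Minimum, if the recall requirement stays.**
- Compute receipt and reading over all KwikPen prescribers who answered Q14: the Analysis Set plus those terminated at Q14 for non-recall, the latter counted as not known to have read. The screener data already retained are enough.
- State in 6.7.4 and in the report that the knowledge results and the effectiveness conclusion apply to self-reported recallers only.

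**Cost.** The preferred option is one programming change and a few sentences on eligibility and denominators; the minimum is wording only. Under either, reported receipt and reading may be lower; under the preferred option, reported knowledge may be too. The preferred option also makes more of the 1,000 invitees eligible, which helps reach 200 completed surveys.
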